[name]

Official Title: Use of protamine for heparin reversal after catheter ablation of atrial fibrillation

NCT Number: NCT03140631

Date of Approval: 10/18/2017

Title: Use of protamine for heparin reversal after catheter ablation of atrial fibrillation: A randomized trial

Introduction:

Catheter based ablation is a well-established and highly effective treatment for atrial fibrillation and the use of such therapies are increasing [1, 2]. To mitigate the risk of intraprocedural thromboembolism, intravenous heparin is administered to maintain an activated clotting time(ACT) of >300s [3]. At the completion of a procedure it can take several hours for a patient's ACT to normalize and for sheaths to be removed. However prolonged sheath presence may increase the risk of vascular complications which may not be infrequent (up to 6-9%) and can be associated with morbidity and increase in costs. A common strategy is to administer protamine sulfate to rapidly (within 5min) neutralize the effect of heparin to expedite sheath removal and patient ambulation and length of stay. Both of these approaches are standard of care practices, have been widely used and reported as case series. However, despite wide-spread clinical use, these two approaches have not been evaluated in a prospective, randomized manner. The objective of this study is to evaluate the safety, efficacy and efficiency of rapid anticoagulation reversal with protamine sulfate versus routine ACT monitoring in patients undergoing catheter based ablation of atrial fibrillation.

Background:

Protamine Sulfate:

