Protamine has been used to facilitate in-laboratory sheath removal after percutaneous coronary interventions for over twenty years [4] and has been shown to decrease time to ambulation without increased rates of thrombosis or access site complications[5]. Protamine reversal of heparin anticoagulation also has an established track record in patients undergoing peripheral endovascular intervention[6] and is used commonly after cardiopulmonary bypass as well[7]. Protamine sulfate is a highly basic protein that forms stable compounds with acidic heparin to neutralize the anticoagulation effects and is itself not a procoagulant agent[8]. While randomized trials and larger studies are needed, it has not been shown to significantly increase rates of post-procedure thrombosis [4-7, 9, 10]. Further catheter ablation for atrial fibrillation is performed via venous approach and under **uninterrupted anticoagulation**.

Protamine can cause hypersensitivity reactions leading to rash, hypotension, pulmonary edema, and cardiovascular collapse[8]. Chilukuri et al reported on 242 patients undergoing atrial fibrillation ablation who received protamine for sheath removal and reported adverse reactions to protamine in 1.2% of cases which was similar to prior reports of protamine exposure[11].

Vascular Complications after ablation procedures:

Vascular access for ablation procedures can be complicated often requiring multiple venous access sites and long procedure and patient flat-time. These factors are known to be associated with increased rates of vascular complications [12, 13]. Patient specific factors, such as the use of antiplatelet agents and female gender, can increase the risk as well[14]. Newer technologies such as cryotherapy techniques require placement of large diameter sheaths which may raise the risk of vascular access complications [12]. Bleeding and thromboembolic complications after atrial fibrillation ablations are common and have been on the rise, predominantly due to increased vascular access complications [15]. Current guidelines recommend intraprocedural heparin be administered prior to or immediately following transeptal puncture [3] and this periprocedural anticoagulation may contribute to the rate of vascular access site complications [9]. A large study of Medicare beneficiaries reported the incidence of any vascular complication from AF ablation to be 6.9%[15] in 2006 up from 5.4% in 2001[15].

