The objective of this study is to evaluate the safety, efficacy and efficiency of rapid anticoagulation reversal with protamine sulfate vs routine ACT monitoring in patients undergoing catheter based ablation of atrial fibrillation. We hypothesize that the routine use of protamine sulfate will facilitate early sheath removal, early ambulation, and improve patient comfort with a significant decrease in the rate of vascular access site complications and time to ambulation. The primary study endpoint will be the 30-day occurrence of vascular access site complications (major or minor groin bleeding including hematoma formation, aneurysm, pseudoaneurysm, AV fistula, deep venous thrombosis).

Methods and Study Protocol:

Study design:

Single center, controlled, prospective, superiority, parallel-group, open-label, randomized clinical trial.

Study Site:

Electrophysiology laboratories and outpatient clinics at the University of Michigan Health System Frankel Cardiovascular Center.

Study Population and Enrollment:

Adult patients undergoing clinically indicated RFA or cryoballoon ablation for atrial fibrillation or atrial flutter (left atrial) will be prospectively enrolled. Consideration for enrollment and obtainment of patient consent will be performed in the pre-operative setting in the cardiac procedures unit prior to the ablation procedure. Consent will be obtained by the study coordinator using both verbal and written study information.

Inclusion Criteria:

- Patient's referred for RFA or cryoablation for atrial fibrillation or atrial flutter (left atrial).
- Age ≥ 18 year
- Patients who are mentally and linguistically able to understand the aim of the trial, comply with the trial protocol, verbally acknowledge the risks, benefits, and alternatives in this trial.

Exclusion Criteria:

- Previous intolerance or allergy to heparin products.
- Current or prior administration of protamine products
-
- History of femoral access site complications including hematoma, AV fistula, pseudoaneurysm, aneurysm.
- Known lower extremity venous thrombosis.
- Coagulopathy or blood dyscrasias.
- Active malignancy.
- Thrombocytosis (platelet count $>600k/\mu l$) or thrombocytopenia (platelet count $<100k/\mu l$)
- Planned use of vascular closure device

Randomization:

A randomization will be performed in a block manner. Patients will be randomized to one of two parallel treatment strategies, namely protamine sulfate group or standard sheath removal group (control).

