Pre-Procedural and Procedural Management:

A pre-procedure groin and lower extremity examination will be documented. Patients on warfarin will continue on uninterrupted therapeutic anticoagulation through the procedure. Patients on direct-acting oral anticoagulants will discontinue the medication one dose prior to their procedure and will resume taking it after hemostasis has been achieved post-procedurally. Prior to heparin administration, ACT will be checked as a target for anticoagulation reversal prior to sheath removal.

Patients will undergo routine pre-procedural assessment and selection of radio frequency ablation (RFA) or cryoablation at the discretion of the treating physician. Procedural endpoints and ablation targets (i.e. pulmonary vein isolation, targeting of complex atrial fractionated electrograms, linear ablation lines, et cetera) are not specified by this protocol and will be performed at the discretion of the treating physician and in accordance with the ablation method selected. An intraprocedural targeted ACT of 300-400s is recommended in accordance with the current guidelines.

Vascular access will be obtained using fluoroscopic and ultrasound guidance using the standard modified-Seldinger technique. Patients undergoing RFA will have right femoral vein access with the use of two 8.5F long-sheaths and one 8F short-sheath. Patients undergoing cryoballoon ablation will have right or both femoral vein access with the use of a 14F long-sheath and 8F short sheath.

Postprocedural management:

Patients randomized to the intervention group will receive a test dose of protamine sulfate 0.5 mg with close monitoring for adverse reactions. If no reactions occur after 5 minutes patients will continue with the intervention group or otherwise undergo routine sheath removal. Protamine sulfate dose will be determined by the amount of heparin received during the last hour of the procedure (1mg of protamine per 100 units of heparin, maximum of 50 mg) and will be administered over 5 minutes, with close hemodynamic monitoring during and after the infusion. ACT levels will then be monitored with a goal ACT of <200s or return to preprocedural baseline.

The non-intervention group will undergo routine ACT measurements beginning 90min after the cessation of the procedure with a goal ACT<200s or return to preprocedural baseline before sheath removal.

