The primary study outcome will be total time to ambulation; the start time (time zero) will be procedural termination. Secondary endpoints will include the 90-day occurrence of vascular access site complications defined as hematoma formation, aneurysm, pseudoaneurysm, arteriovenous fistula formation, access-site related major bleeding (defined as BARC type 3a or 5[18]), or procedural intervention for access complications (surgical repair, thrombin injection, et cetera). Additional exploratory endpoints will be the time to achieve hemostasis, duration of manual compression, need for repeat manual compressions, the total number of re-bleeding events, patient reported hematoma on 7 day phone call, and patient reported groin pain at discharge, 7 day phone call, and follow up appointment.

Safety endpoints:

Safety endpoints will be thrombotic events defined as stroke or transient ischemic attack, deep vein thrombosis, pulmonary embolism, lower extremity thromboembolic events, acute myocardial infarction, or death. There is no plan for an interim analysis.

Statistical Analysis:

Based on preexisting studies and an audit of quality data from our own laboratory, we anticipate a baseline time-to-ambulation of 360 ± 180 min with a reduction to 270 min with the use of protamine. We estimate that the enrollment of 150 patients would provide 80% power to detect the anticipated difference in the primary outcome at the 5% two-sided level of significance, assuming a 10% loss to follow up. Prespecified sub-groups for secondary analysis include sex, age, clinical comorbidites (BMI, diabetes, CHF), ablation method, use of antiplatelet medications, prior ablation procedure, prior coronary angiography or intervention.

Data will be reported as means and standard deviations or as absolute values and percentages where appropriate. The Chi Square and Fisher's exact test will be used to compare categorical

variables. Unpaired or paired Student's t-test or the Mann-Whitney test will be used as appropriate. A P value less than 0.05 will be considered statistically significant.

Clinical Significance:

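### Safety is a stated objective, but no endpoint identifies a protamine reaction, so a non-fatal reaction that causes no listed event is not a planned safety result

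*Combined protocol and SAP*

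**What the plan says.** The Introduction states: "The objective of this study is to evaluate the safety, efficacy and efficiency of rapid anticoagulation reversal with protamine sulfate versus routine ACT monitoring". Objective and Hypothesis repeats this almost word for word.

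The Safety endpoints section reads: "Safety endpoints will be thrombotic events defined as stroke or transient ischemic attack, deep vein thrombosis, pulmonary embolism, lower extremity thromboembolic events". Acute myocardial infarction and death complete the list, and no general adverse-event category follows.

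On the drug's own harm, the Background (Protamine Sulfate) says: "Protamine can cause hypersensitivity reactions leading to rash, hypotension, pulmonary edema, and cardiovascular collapse". It then cites a series of "242 patients undergoing atrial fibrillation ablation who received protamine for sheath removal and reported adverse reactions to protamine in 1.2% of cases".

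Postprocedural management acts on this risk: "Patients randomized to the intervention group will receive a test dose of protamine sulfate 0.5 mg with close monitoring for adverse reactions". It continues: "If no reactions occur after 5 minutes patients will continue with the intervention group or otherwise undergo routine sheath removal". Hemodynamic monitoring is also required around the full dose, with no stated end time. The Exclusion Criteria include "Current or prior administration of protamine products".

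Data Collection and Analysis refers to an attached data form, which is not in the text available for review. Its follow-up contacts are for thromboembolic events, bleeding and procedural outcomes.

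**The concern.** The investigators foresaw a specific harm of the study drug, cited its frequency, and built a test dose and monitoring around it. Nothing in the endpoint or analysis plan then counts it. A patient could have a non-fatal cardiovascular collapse after protamine, be observed and managed at the bedside, and not be a safety event under the plan as written.

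At stake is the completeness of the safety conclusion. Clinical Significance anticipates that protamine may prove safe and simple and that the results will affect practice and guidelines. The listed endpoints inform the thrombotic, bleeding and access-site parts of that statement. They say nothing about reactions to the drug.

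**Working it through.** **Step 1. Would any endpoint identify a reaction?**

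| Endpoint group | Content | Identifies a reaction? |
|---|---|---|
| Primary | Time to ambulation (Study endpoints); Objective and Hypothesis instead names 30-day access-site complications | No, under either |
| Secondary | 90-day access-site complications, including major bleeding and procedural intervention | No |
| Exploratory | Hemostasis time, compression, re-bleeding, hematoma, groin pain | No |
| Safety | Thrombotic events, myocardial infarction, death | No; a reaction that led to one of these would appear only as that event |

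A test-dose reactor sent to routine sheath removal still contributes to the ambulation, hemostasis, compression, re-bleeding and access-site endpoints. None of them shows that a reaction occurred.

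**Step 2. The cited rate.** 0.012 × 242 = 2.9, so the figure corresponds to about 3/242 = 1.24%. The exact (Clopper-Pearson) 95% interval for 3/242 is 0.26% to 3.6%. The rate covers any reaction, not collapse alone.

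**Step 3. Expected count.** Enrolment is 150 (Statistical Analysis). No allocation ratio is given; assuming 1:1, 150 / 2 = 75 patients receive protamine. Expected count = 75 × p, and the chance of at least one = 1 − (1 − p)^75.

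| Rate p | Expected in 75 | Chance of none | Chance of at least one |
|---|---|---|---|
| 0.256% (lower limit) | 0.19 | 0.825 | 18% |
| 1.2% (cited) | 0.90 | 0.404 | 60% |
| 3.58% (upper limit) | 2.7 | 0.065 | 94% |

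At 1.2%, 50 protamine patients would give 0.6 expected and a 45% chance of at least one (1 − 0.547). With 100 patients the figures are 1.2 and 70% (1 − 0.299).

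**Step 4. What a count could show.** Exact two-sided 95% intervals for 75 patients:

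- 0 reactions: 0 to 4.8% (upper limit 1 − 0.025^(1/75) = 0.0480)
- 1 reaction: 0.03% to 7.2%
- 2 reactions (2.7%): 0.3% to 9.3%

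For an 80% chance of seeing at least one reaction, the true rate would have to be 1 − 0.20^(1/75) = 2.1%. For a 95% chance it would have to be 1 − 0.05^(1/75) = 3.9%.

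**The case against.** The endpoint list has a visible rationale. The objective is framed as protamine against routine ACT monitoring, and the Background treats post-procedure thrombosis as the question still needing randomized data. Thrombosis can be compared between arms. A protamine reaction can occur only in patients given protamine, so it adds nothing to the randomized contrast. This explains why thrombosis leads the list. It does not show that reactions were deliberately left out, and the objective covers safety as a whole.

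A second argument is that the count would be too small to be useful. With 0 of 75, the upper limit of 4.8% is wider than the 3.6% from the cited series, so the trial could not refine the known rate. That stands. The value of the count is transparency about the drug's named harm in this trial, not a better estimate of its rate.

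Third, the unseen form may have a field for reactions, and Statistical Analysis provides for counts and percentages in general. A reaction count might therefore be reported anyway. That is possible, but the sentence on counts and percentages sets a format and does not say which events are counted. A form field would not be a commitment to report.

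A reader might infer that reactions go unwatched or unrecorded. The documents do not support this: monitoring is explicit, and the form cannot be judged. A reader might also take the 60% as the chance of a severe event. It is the chance of any reaction at the cited rate, and no rate for collapse is given.

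**Conclusion.** The concern holds as a gap in endpoints and reporting. A non-fatal protamine reaction that causes no listed event is not a planned safety result, and no endpoint or analysis commits the trial to reporting reactions, although safety is a stated objective.

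The size rests on assumptions: 1:1 allocation, all 75 protamine-group patients receiving the drug, and a cited rate that applies here. On these, about one reaction is expected (0.9), with a wide range for the chance of seeing any. The rate may not transfer, because patients with prior protamine exposure are excluded. The finding itself depends on none of these figures, only on the endpoint text.

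It would go too far to conclude that the specified comparisons are biased or that the sample size is wrong. Neither follows: the 150 patients are sized for time to ambulation, and a reaction count is descriptive. The remark in Clinical Significance that protamine may be safe is also a hedged expectation, not a planned conclusion. The change should be made because it closes part of the trial's own safety question at little cost.

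**What to change.** Add to Safety endpoints, as a descriptive endpoint: protamine reaction (rash, hypotension, pulmonary edema, cardiovascular collapse) after the test dose or during or after the infusion. Before enrolment, the investigators should fix the criteria for relatedness to protamine, the grading as serious or non-serious, and the end of the counting window. The window needs stating because the monitoring after the infusion has no end time. Prior criteria matter because the trial is open-label.

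Add to Statistical Analysis: the number and percentage of patients with a reaction, including test-dose reactions, will be reported with an exact 95% confidence interval among patients randomized to the protamine group who received any protamine. Any reaction in a control patient given protamine for clinical need will be listed separately. This keeps the denominator to the group for which Postprocedural management specifies the monitoring.

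The cost is one endpoint line, a short analysis statement, a brief set of criteria, and a form field if the form lacks one. Sample size, planned comparisons and clinical management do not change. There are three downsides. The estimate will be imprecise. Attribution is by unblinded staff with no control-arm count, so some hypotension from other causes may be ascribed to protamine. The reported safety profile may also look less favourable.

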The University of Michigan is a high-volume ablation center with particular expertise in treating atrial fibrillation using both radiofrequency and cryoballoon ablation techniques. The Cardiac Arrhythmia Service performs approximately 1,100 ablation procedures per year including nearly 700 procedures for atrial arrhythmias primarily for atrial fibrillation. Protamine has not been incorporated into routine lab protocols for post-procedure care and is administered based on operator preference. Owing to the very low risk of significant complications specifically embolic events (<0.5%) over the years with the current approach, protamine has not been routinely used unless there is a clinical need. However, published case series suggest that protamine can safely be utilized to expedite vascular hemostasis. Therefore there is both a scientific and clinical need to determine whether each approach is comparable and whether one is superior to the other. There already is sufficient body of literature from this and other institutions demonstrating the utility of either approach.

A brief audit of recent procedures shows that in cases where rapid reversal with protamine is not used, the average time from patient arrival to the post-procedure unit to sheath removal is 204 ± 47 minutes; this delay is nearly entirely attributed to the time required for the critical

decrease in ACT to allow safe sheath removal. This prolongs patient time to ambulation and may contribute to outcomes.

Summary:

The use of protamine sulfate for rapid heparin neutralization and early sheath removal after catheter based therapies has been used with good results in a variety of clinical settings. However, much of the safety and efficacy data are derived from small, non-randomized, and retrospective series and have been performed in patients undergoing coronary and vascular interventions involving single vessel access. Ablation procedures involve the use of more vascular access, larger diameter sheaths, prolonged procedure times, more intensive anticoagulation protocols, and carries the risk of ablation lesion related thrombosis[3] which limits the applicability of the existing data. The few studies examining the use of protamine for atrial ablation have all been small, non-randomized cohorts but have suggested improved vascular access outcomes as well as decreased time to patient ambulation. Randomized prospective data are needed to corroborate these findings.

Objective and Hypothesis:

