Manual compression using the standard technique by professional staff, will be applied until hemostasis is achieved, followed by a 6-hour period of flat time before ambulation. Patients will be monitored overnight for post-procedural observation which is the current standard of care in our laboratory.

Immediately after the sheath removal and the morning after the procedure, detailed examination of both groins will be performed for signs of bleeding, hematoma, aneurysm, or fistula as standard of care and will be carefully documented. Patients with signs or symptoms of vascular complications will undergo duplex venous ultrasound as usual standard of care. In addition Hemoglobin and hematocrit levels will be documented before and the morning after the procedure as per routine clinical care protocol.

Post-procedural anticoagulation will be administered for at least two months per national guideline recommendations; choice of anticoagulation and duration beyond two months will be at the discretion of the treating physician.

Data Collection and Analysis:

Baseline demographic, clinical, procedural and ultrasound data will be collected. Patients will be monitored overnight post procedure (18-24 hours) with routine assessment of clinical access site, neurologic checks, and patient comfort scores. Patients will have one-week phone follow up and three month clinical visits to assess thromboembolic and bleeding events as well as procedural outcomes. Data collection formed is shown (see attached form).

Vascular ultrasound will be obtained if clinically indicated as described above. Results will be interpreted by two independent, qualified readers to ensure standardization and accuracy. Discrepant interpretations will be jointly reviewed for agreement.

Study endpoints:

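### The planning means for time to ambulation (360 min control, 270 min protamine) lie at least 90 min below the earliest times that the protocol's own 6-hour flat-time rule and time zero allow

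*Combined protocol and SAP*

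**What the plan says.** Four parts of the combined protocol and SAP bear on this.

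- **Endpoint (Study endpoints).** The primary outcome is total time to ambulation, and "the start time (time zero) will be procedural termination".
- **Flat time (Postprocedural management).** Manual compression "will be applied until hemostasis is achieved, followed by a 6-hour period of flat time before ambulation". The rule is not restricted to one arm.
- **Steps before sheath removal (Postprocedural management).** Protamine patients first have a test dose: "If no reactions occur after 5 minutes patients will continue with the intervention group or otherwise undergo routine sheath removal". The full dose then "will be administered over 5 minutes, with close hemodynamic monitoring during and after the infusion". Control patients have "routine ACT measurements beginning 90min after the cessation of the procedure", and their sheaths stay in until the ACT goal is met.
- **Sample size (Statistical Analysis).** Citing earlier studies and a local audit in general terms, the plan states that "we anticipate a baseline time-to-ambulation of 360 ± 180 min with a reduction to 270 min with the use of protamine". It concludes that 150 patients give 80% power at the two-sided 5% level, allowing 10% loss to follow-up.

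The only audit time shown is under Frankel Cardiovascular Center Experience, for cases without protamine: "the average time from patient arrival to the post-procedure unit to sheath removal is 204 ± 47 minutes".

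**The concern.** The endpoint clock contains the whole flat time. Any patient managed as the protocol requires must therefore have a value above 360 min, whichever arm they are in. The planned protamine mean of 270 min is shorter than the flat time by itself. The planned control mean of 360 min equals it, which leaves nothing for the ACT to fall, for sheath removal or for compression.

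These means, with the SD of 180, are the only inputs given for the sample size. As written they describe a course that the protocol does not permit, and a reader cannot tell which statement is the mistake: the planning figures, the flat-time rule or the choice of time zero. The matter concerns the primary outcome of an open-label trial, where the rule for when a patient may walk needs to be unambiguous. The randomized comparison and the type I error are not affected.

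**Working it through.** **1. Reproduce the plan's figure.** Inputs from Statistical Analysis: means 360 and 270, SD 180, two-sided 5%, 80% power, 10% loss. Assumed here: 1:1 allocation and the same SD in both arms, since neither is stated.

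- Standardized difference: (360 − 270)/180 = 90/180 = 0.50.
- Two-sample t-test: 64 per arm, 128 evaluable; 128/0.9 = 142.2, so 143 enrolled.
- Allowing for the Mann-Whitney test (efficiency 0.955): 63.77/0.955 = 66.8, so 67 per arm, 134 evaluable; 134/0.9 = 148.9, so 149 enrolled.
- Power with 150 × 0.9 = 135 evaluable (67.5 per arm): 82.2% by t-test, 80.4% by Mann-Whitney.

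The stated 150 and 80% follow from the stated inputs. The arithmetic is sound.

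**2. Earliest times the protocol permits, from procedural termination.** These are minimum times, before any compression time, and not expected means.

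| Arm | Components (min) | Earliest | Planned mean | Shortfall |
|---|---|---|---|---|
| Protamine, dosing not counted | 360 flat | 360 | 270 | 90 |
| Protamine, dosing after time zero | 5 + 5 + 360 | 370 | 270 | 100 |
| Control | 90 + 360 | 450 | 360 | 90 |

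The 360-min row is the firm minimum for protamine. The 370-min row also needs the test dose to start at or after time zero, and the protocol gives no start time for it. A patient who reacts to the test dose goes over to routine sheath removal, which can only lengthen the time.

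**3. What the stated inputs would imply.** Under a normal model with SD 180, the share walking before 360 min is Φ((360 − 360)/180) = 50% of controls and Φ((360 − 270)/180) = Φ(0.5) = 69% of protamine patients. Under the flat-time rule both shares should be zero.

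**4. Does the conflict carry into power?** Power depends on the difference and the SD. A flat time common to both arms adds the same 360 min to each mean and cancels, so means that are too low do not by themselves make 90 or 180 wrong. The documents do not fix the true difference, so a range is shown (t-test, 135 evaluable; differences and SDs are illustrative assumptions apart from the plan's 90/180):

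| Difference (min) | SD (min) | Power |
|---|---|---|
| 80 (gap between the minimum times, 450 − 370) | 180 | 73% |
| 90 (plan) | 180 | 82% |
| 144 | 180 | 99.6% |
| 114 | 240 | 78% |
| 144 | 240 | 93% |

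At SD 180 the smallest difference with 80% power is 0.4858 × 180 = 87.4 min, only just below the planned 90.

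The 144 comes from adding the audited 204 to 360 (564 min for control) and assuming protamine sheaths come out 60 min after time zero (420 min): 564 − 420 = 144. The 114 uses 90 min instead: 564 − 450 = 114. Both use an audit interval that starts at arrival in the post-procedure unit, so transfer and compression are left out.

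**The case against.** The strongest reply is that nothing of consequence has been shown. The sample size rests on the difference and the SD, the flat time cancels, the calculation reproduces, and nobody is asking for more patients. All of that stands, and it limits the point to inconsistent inputs. It does not remove the point: the 90 min is given only as the gap between two means that cannot occur, and no other support for it is shown.

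A second reply is that the plan names its basis (earlier studies and a local audit), so the figures may come from settings with shorter bed rest. That is possible. That these data are not reprinted is a gap in reporting, not a contradiction. But figures from shorter bed rest would need adjusting before being applied to an endpoint that includes 6 hours flat.

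Three stronger readings are tempting, and the documents support none of them.

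- *The trial is underpowered.* The 73% case uses the gap between two minimum times, which is not an expected difference.
- *Power is certainly ample.* A reader might combine the audited 204 min with prompt protamine sheath removal and conclude that power is at least 99.6% at SD 180, or at least 93% at SD 240. These are not lower bounds. The audit has no protamine arm and runs on a different clock, and the protamine removal time is assumed. Moving that time from 60 to 90 min at SD 240 brings power to 78%.
- *Patients are being walked before the protocol allows.* The planning means alone are no evidence of how patients are managed.

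**Conclusion.** The conflict is definite and should be corrected. Given time zero at procedural termination and 6 hours flat after hemostasis, the planned protamine mean is 90 min below the firm minimum (100 min if dosing follows time zero), and the planned control mean is 90 min below its minimum of about 450. These are understatements of at least that size, because compression and any further wait for the ACT to fall come on top.

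This rests only on the protocol's own text, read as applying the flat time to both arms and requiring the control ACT check before sheath removal. It does not show that 80% power or the sample size of 150 is wrong. The direction of any power error is unknown, because the documents give no between-arm difference and no SD measured from procedural termination to ambulation. The power figures also assume 1:1 allocation and a common SD.

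**What to change.** Decide which statement is the intended one, then do one of the following.

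1. **If the 6-hour flat time and time zero stand:** in Statistical Analysis, restate both arm means, the difference and the SD on the clock from procedural termination to ambulation, with the flat time included. Give the source of each value or label it an assumption. Restate the power for 150 enrolled (135 evaluable) over a range of differences and SDs and not as a single figure. A power statement that splices the audited sheath-removal time with an assumed protamine removal time should not go into the protocol as a lower bound.
2. **If 360 and 270 min describe the intended course:** correct the flat-time rule in Postprocedural management or the time zero in Study endpoints.

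The first route costs one recalculation and about two rewritten sentences. The second costs a short protocol amendment. Neither calls for a change in enrolment.
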